5.0 Inclusion and Exclusion Criteria/ Study Population

Inclusion Criteria

All patients over the age of 18-years with suspected upper gastrointestinal bleed (GIB) due to esophageal varices and in whom octreotide is initiated will be eligible.

Inclusion Criteria:

1. Adult males and females who are 18 years of age or older.
2. Evidence or suspicion of upper GIB at presentation defined as either:
 - a. Patient presenting with melena or hematemesis
 - b. Patient presenting with bright red blood per rectum, along with hypotension (systolic blood pressure <90mmHg and diastolic blood pressure <60mmHg) and tachycardia (heart rate >155 beats per minute)
3. Patient with known or suspected cirrhosis:
 - a. Historical biopsy indicating cirrhosis
 - b. Suspected cirrhosis defined as both:
 - i. Clinical data (ex: platelets less than 120,000/L)
 - ii. Nodular liver on ultrasound, computed tomography (CT), or magnetic resonance imaging (MRI)
4. Upper GIB secondary to bleeding esophageal varices as show by esophageal endoscopy, requiring endoscopic band ligation (EBL) at presentation
5. Willing and able to provide informed consent for study.

Exclusion Criteria

1. Known upper gastrointestinal malignancy
2. Bleeding from gastric varices, with or without esophageal varices
3. Use of any other endoscopic method to stop GI bleeding beyond endoscopic band ligation, including injectables such as sclerosants, epinephrine, saline, endoscopic clips, endoscopic suturing, etc.
4. Variceal bleeding in the last 90 days
5. History of TIPS or vascular decompression surgery
6. Pregnant females
7. Incarcerated individuals
8. Myocardial infarct, cerebrovascular accident, sepsis, respiratory failure, or severe intercurrent illness within the previous 6 weeks
9. Non-cirrhotic portal hypertension causing esophageal varices
10. Known or suspected allergy to octreotide

Linkages to subjects: Sequential numbers will be assigned to patient information collected and entered into a database. Patient identifiers will be stored separately (with the informed consent forms) from extracted data – with data code-linked to identifiers. Only study staff personal at the institution where the patient has been enrolled will have access to PHI. Therefore, while patient data will be stored on the secure server where MUSC study staff will have access the patient identities from other sites will not be stored here. This is to keep the patients identities confidential. All records will be kept on a secure server that will be erased six years after the completion of the study.

6.0 Number of Subjects

We anticipate enrolling approximately 40 subjects at the local MUSC site, with a goal of 160 patients for the entire study)

8.0 Recruitment Methods

Cirrhosis patients presenting with suspected upper GI bleeds presenting to the involved hospital sites are always seen by consultant – either the attending or fellow – from the Gastroenterology and Hepatology Services. Therefore, identification of potential subject for the study will be through chart reviews of current inpatients by the consult and study team and by consult requests to the GI/Hepatology team. All members of the study team can access the consult lists as well as inpatient lists for individuals presenting with upper GIB and all consult team members and study team members will be added as additional study members to this protocol in order to have IRB-approval to recruit subjects.

9.0 Consent Process

This research study will involve obtaining informed consent from potential subjects.

The need for endoscopic therapy cannot be anticipated, so informed consent will be obtained prior to endoscopy from the patient when appropriate, upon presentation to MUSC with a suspected variceal bleed. Potential patients will be approached for participation in this study by a member of the IRB-approved study team and the informed consent form and HIPAA form will be reviewed – verbal review and a written/printed consent available for review with the subject.

Ample time will be allocated between informing the prospective participant and obtaining written consent will vary but will ultimately depend on how long the potential participant requires for all his/her questions to be answered to the best of the study team's ability.

Additionally, the patient will have time to read the consent and HIPAA forms on their own prior to discussing with research staff.

10.0 Study Design / Methods

This prospective and randomized controlled trial will involve administration of either octreotide infusion for 24-hours (Group A) or for 72-hours (Group B). This study involve the following:

Screening

Esophageal varices as the sole cause of upper gastrointestinal (GI) bleeding will need to be confirmed. Endoscopic band ligation will be performed per standard of care when deemed appropriate by the treating physician.

During this time, and regardless of participation in the research study, octreotide will be administered per standard-of-care before endoscopy. Endoscopy with band ligation will be performed per standard-of-care, if needed. Not all patients may have variceal bleeding and even if varices are present, not all may need EBL. Only patients who receive EBL for varices with stigmata of bleeding will be randomized for the study, to receive octreotide infusion for 24- or 72-hours after successful EBL. Subsequent care will be per the primary team and not affected by participation in the study.

Treatment:

Randomization will be conducted for all enrolled subjects at all site by the study coordinator and coinvestigators at MUSC. Only after undergoing EBL will patients be randomized by computer-generated blocked randomization for treatment allocation. The randomization schedule will be blinded in sequentially numbered opaque envelopes.

Patients will be randomized to receive octreotide as a continuous intravenous infusion for 24-hours or 72-hours after the infusion is started. Following standard-of-care for variceal bleeding, all patients will be monitored in the hospital for at least 72-hours after undergoing esophagogastroduodenoscopy (EGD) and EBL. Any recurrent bleeding will be managed per standard-of-care, which may include a combination of octreotide infusion, placement of an esophageal balloon tamponade tube (i.e. Minnesota tube, or similar), repeat endoscopic intervention, referral to Interventional Radiology for transjugular intrahepatic portacaval shunt (TIPS), or surgery.

Follow-Up:

The follow-up of this study will take place until 1-year after the initial bleeding episode and information will be collected via chart reviews of the medical records and follow-up phone calls at: 30-days, 60-days, 90-days, 180-days, and 1-year after the initial visit. Phone calls will take

approximately 15 minutes and will consist of questions regarding the patients general health status, cirrhosis related health complications and possible side effects of octreotide.

Collected Data:

Additional data collected from medical records during this study will include:

1. Patient demographics including race and ethnicity
2. Presenting symptoms and physical exam findings
3. Past medical history
4. Laboratory results – complete blood count (CBC), liver function tests, ammonia (if checked per hospital standard of care), hepatitis serologies
5. Imaging findings – liver morphology, patency of portal vein
6. Medications – outpatient and during admission
7. Paracentesis
8. Use of antibiotics
9. Time to endoscopy
10. Endoscopic findings
11. Endoscopic treatment
12. Thirty, 60, 90, 180-day and 1 year follow-up will gather the following information as available:
 - a. Patient alive or not
 - b. Laboratory results – complete blood count (CBC), liver function tests, ammonia (if checked per hospital standard of care), hepatitis serologies
 - c. Medication
 - i. Betablockers
 - ii. Antibiotics
 - d. Rebleeding
 - e. Endoscopic findings and treatment

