1.0 Objectives / Specific Aims

The objective of this study is to determine the safety and efficacy of 24-hours vs. 72-hours continuous infusion of octreotide after successful endoscopic treatment of esophageal varices and overt gastrointestinal bleeding.

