2.0 Background

Esophageal variceal hemorrhage due to portal hypertension is a dreaded clinical complication in patients with cirrhosis and is associated with significant morbidity and mortality.¹ It is usually managed with pharmacologic, endoscopic, and radiological techniques, and sometimes surgery.¹ The current standard of care includes intravenous infusion of the somatostatin analogue, octreotide, which is usually started as soon as variceal hemorrhage is suspected, followed by urgent or emergent endoscopy, and treatment typically with band ligation (EBL) within 8 to 24 hours.^{1,2} Intravenous octreotide is then continued for three, and up to five days, although currently available guidelines are not clear on the appropriate duration of therapy.

The rational for using octreotide is that it reduces portal blood flow, which reduces portal pressure, and hence reduces the propensity for variceal bleeding. The pharmacology of octreotide suggests that the benefits are transient due to desensitization and/or tachyphylaxis.³ The appropriate duration of continuous octreotide infusion is uncertain and largely based on expert opinion. Prolonged infusion of octreotide is thus likely to be unnecessary, and may inappropriately increase hospital and medical costs.

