3.0 Intervention to be studied (if applicable)

The study will be a prospective, randomized-controlled multi-center study.

- Patients with overt, or active, variceal bleeding will be randomized to octreotide infusion for either 24-hours or 72-hours following successful endoscopic band ligation (EBL).

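### The Treatment paragraph counts the 24 or 72 hours from an ambiguous start of infusion, while the objective, the intervention section and the Screening paragraph count from successful endoscopic treatment or EBL

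*Combined protocol and SAP*

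**What the plan says.** Three statements set the clock at endoscopic treatment:

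- Section 1.0 (Objectives): "24-hours vs. 72-hours continuous infusion of octreotide after successful endoscopic treatment of esophageal varices".
- Section 3.0 (Intervention): "octreotide infusion for either 24-hours or 72-hours following successful endoscopic band ligation (EBL".
- Section 10.0, Screening: "to receive octreotide infusion for 24- or 72-hours after successful EBL".

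One statement sets it differently. Section 10.0, Treatment: "Patients will be randomized to receive octreotide as a continuous intravenous infusion for 24-hours or 72-hours after the infusion is started".

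Four further statements bear on what the start of the infusion means:

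- Section 10.0, Screening, applies to patients whether or not they take part: "octreotide will be administered per standard-of-care before endoscopy".
- Section 2.0 describes standard care as an intravenous infusion "which is usually started as soon as variceal hemorrhage is suspected". After endoscopy, "Intravenous octreotide is then continued for three, and up to five days".
- Section 10.0, Treatment: "Only after undergoing EBL will patients be randomized".
- The primary endpoint in section 4.0 is rebleeding in the 72 hours from hemostasis with EBL. The in-hospital monitoring period in section 10.0 also runs from endoscopy and EBL.

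**The concern.** The start of the clock is part of the definition of the randomized treatment, and the Treatment paragraph is where a site would look to decide when to stop the pump. By then the patient has normally been on octreotide since before endoscopy. The protocol does not describe that infusion ending, or a new one beginning, at EBL. A site could reasonably take the start of the infusion to be the time octreotide was first hung.

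A site reading it that way would deliver a shorter post-EBL course than the objective names, in both arms. If other sites counted from EBL, the trial would mix two regimens under the same arm labels. Meanwhile the primary endpoint window would stay fixed at 72 hours from EBL, so treatment and outcome would run on different clocks.

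**Working it through.** **Inputs.** Assigned durations of 24 and 72 h (sections 1.0, 3.0, 10.0). Primary window of 72 h from hemostasis with EBL (section 4.0), taken here to begin when EBL is complete. Delay d from infusion start to EBL: not fixed anywhere in the protocol. For illustration only, d = 8 and d = 24 are borrowed from the usual-care time to endoscopic treatment in section 2.0. Those are upper limits in background text with no stated starting point, so d may well be shorter than 8 h; d = 0 is included as the other end.

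**The plan's own figure.** Section 11.0 gives 69 per group for 90% success in both arms, a 15-point margin, type I error 0.05 and 90% power. With unpooled variance and one-sided 0.05:

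n = (1.645 + 1.282)² × (0.9 × 0.1 + 0.9 × 0.1) / 0.15² = 8.567 × 8 = 68.5, rounded up to 69.

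The figure reproduces. Neither d nor the infusion time enters the formula, so 69 does not depend on which clock is used.

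**Post-EBL octreotide if the clock starts before EBL** (d up to 24 h):

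- Short arm = 24 - d; long arm = 72 - d.
- Contrast = (72 - d) - (24 - d) = 48 h.
- Primary window: both arms on drug for 24 - d, only the long arm on drug for 48, both arms off drug for d. The sum is 72.

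| Assumed d (h) | Short arm after EBL (h) | Long arm after EBL (h) | Both on / long arm only / both off (h) |
|---|---|---|---|
| 0 | 24 | 72 | 24 / 48 / 0 |
| 8 | 16 | 64 | 16 / 48 / 8 |
| 24 | 0 | 48 | 0 / 48 / 24 |

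**If the clock starts at EBL**, every patient has 24 or 72 h after EBL whatever d is, and the split is 24 / 48 / 0.

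**Total octreotide under an EBL clock**, including the pre-EBL part, is 24 + d and 72 + d: 32 and 80 h at d = 8, 48 and 96 h at d = 24.

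**The case against.** The best defence is grammatical. In the Treatment sentence the infusion can refer back to the continuous infusion that patients are randomized to receive. Randomization happens only after EBL, so that infusion would begin after EBL and there would be no conflict. The surrounding text supports this: the preceding paragraph says after EBL, and the endpoint and the monitoring period run from EBL. The earlier clock also gives an odd result, since at d = 24 a short-arm patient would be randomized to a regimen already finished. The Screening paragraph says only that octreotide is administered before endoscopy; that it is an infusion which is then continued comes from the background section.

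Much of this stands. It makes the post-EBL reading plausible, and under that reading nothing changes. What remains is that the reading has to be inferred. No text says how the pre-EBL infusion passes into the assigned one. Sections 11.0 and 14.0 mention 24 hours of octreotide without a starting point, so they do not settle it. In a multi-center trial, stop times should not rest on each site's inference.

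A reader might go further and infer that the sentence plainly contradicts the objective, that sites will use the earlier clock, or that the comparison is biased. The documents do not support this. The wording admits both readings, and nothing shows which one sites use. The delay d is also settled before randomization, so under a common clock it is balanced between arms in expectation. Nor can the 16 to 0 h range be read as what patients will receive, because it rests on a borrowed value of d.

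**Conclusion.** The point holds as an ambiguous and inconsistent time origin in the operative dosing sentence. It should be fixed, with medium confidence.

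Its size depends on the reading. It is zero if the phrase means the infusion assigned after EBL. It is a loss of d hours of post-EBL octreotide in each arm if a site counts from the pre-EBL start, with d unknown. In that case the short arm gets less than the 24 post-EBL hours in the objective, and the long arm is off drug for the last d hours of the primary window. The risk is a changed intervention, or different regimens at different sites. With one clock used throughout, the 48-hour contrast is preserved for d up to 24 h and the sample size of 69 per group is unaffected.

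**What to change.** In section 10.0, Treatment, replace the closing phrase on duration with: *for 24 hours or 72 hours after completion of successful EBL*. This agrees with sections 1.0 and 3.0, the Screening paragraph, the point of randomization and the endpoint clock in section 4.0.

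The cost is one phrase, with no change to sample size, endpoint or visits. The small downside is that total octreotide exposure then varies by patient with the pre-EBL time (24 + d and 72 + d hours). If the sponsor in fact meant total infusion time, the three EBL-based statements would have to change instead.

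Optionally, record infusion start and stop times in the REDCap project. Section 10.0 already plans to collect time to endoscopy and medications during admission, but does not itemize infusion times. Adding them would let adherence to the clock be checked, at the price of minor data entry.

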4.0 Study Endpoints (if applicable)

Primary Endpoint:

- Rebleeding within 72-hours after control of hemostasis with EBL

Secondary Endpoints:

- Rebleeding within 7 and 30-days
- Survival within 7 and 30-days
- Complications from octreotide, including, but not limited to: pneumonia, cardiac complications (arrhythmias, heart failure, cardiac ischemia), paralytic ileus, hyperglycemia, diarrhea, abdominal pain, nausea

Rebleeding within 72-hours will be defined as any of the following:

- A drop in hemoglobin by more than 20 percentage points from baseline
- Sustained tachycardia above 100 beats per minute, with or without hematochezia or melena
- Transfusion of >2 unites packed red blood cells after EBP
- Recurrence of hematemesis or ongoing melena
- Urgent or emergent need for Transjugular Intrahepatic Portosystemic Shunt (TIPS)." to control suspected rebleeding

Rebleeding after 72-hours will be defined as:

- Any new episode of hematemesis, melena, or hematochezia (with hemodynamic instability)
- Drop in hemoglobin by more than 20 percentage points OR the need for >2 units packed red blood cells
- Need for TIPS or surgery to control suspected bleeding

Patients who rebleed will be treated per hospital standard of care and physician preference. Treatment of rebleeding will be recorded.

Follow-up Endpoints:

Thirty, 60, 90, 180-day, and 1-year follow-up.

Rebleeding after 72-hours will be defined as:

- Any new episode of hematemesis, melena, or hematochezia (with hemodynamic instability)
- Drop in hemoglobin by 20 percentage points OR need for >2 units packed red blood cells
- Need for TIPS or surgery to control suspected bleeding

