After 25, 50, and 75% of the research subjects are enrolled in the study an independent, internal data safety and monitoring board (DSMB) meeting in which we will present accrual and safety data to group members. If the accrual rate is not reached, we will conduct a DSMB meeting at least semi-annually. The DSMB will review any SAEs as they occur. The DSMB will be composed to non-study associated members, specifically: 2 gastroenterologists and 1 statistician at the Lead Investigating Site (MUSC) and it will be responsible for reviewing the data at all sites individually and the data for the study as a whole.

All adverse events including incidences of bleeding in both the control and experimental group will be recorded and submitted to the Institutional Review Board (IRB) within 10 business days. If a serious adverse event occurs, this will be reported to the IRB within 2 business days. The descriptions and definitions of adverse or serious adverse events will be followed and if any adverse events occur, we will report these to the IRB.

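### The safety endpoint counts complications attributed to octreotide, with no masking described, no common counting window and no listed glucose or complication item; any-cause counts over one fixed window would be cheap and less open to bias

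*Combined protocol and SAP*

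**What the plan says.** Section 1.0 puts safety beside efficacy: "The objective of this study is to determine the safety and efficacy of 24-hours vs. 72-hours continuous infusion of octreotide". Section 4.0 turns this into a secondary endpoint: "Complications from octreotide, including, but not limited to: pneumonia, cardiac complications (arrhythmias, heart failure, cardiac ischemia), paralytic ileus, hyperglycemia, diarrhea, abdominal pain, nausea". It gives no thresholds, time window or assessor. Section 11.0 then plans to look for factors associated with complications, so they must exist as an analysis variable.

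The data list in section 10.0 opens with "Additional data collected from medical records during this study will include". Its laboratory entry is "complete blood count (CBC), liver function tests, ammonia (if checked per hospital standard of care), hepatitis serologies", and the follow-up sub-list repeats the same tests. Neither the admission items (1 to 11) nor the follow-up items (12a to 12e) include glucose, a complication or an adverse event.

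Follow-up uses chart review and "follow-up phone calls at: 30-days, 60-days, 90-days, 180-days, and 1-year after the initial visit". The calls cover general health, "cirrhosis related health complications and possible side effects of octreotide".

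Two provisions support in-hospital capture. Section 10.0 says "all patients will be monitored in the hospital for at least 72-hours after undergoing esophagogastroduodenoscopy (EGD) and EBL". Section 13.0 says "All adverse events including incidences of bleeding in both the control and experimental group will be recorded and submitted to the Institutional Review Board (IRB"). The deadline for these reports is 10 business days, and the DSMB is to review serious events as they occur.

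On masking, section 10.0 calls only the randomization schedule blinded. It describes neither a placebo infusion nor a masked assessor.

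**The concern.** Pneumonia, hyperglycemia, nausea and abdominal pain can also occur in bleeding cirrhotic patients without octreotide. An endpoint limited to complications from the drug therefore needs someone to judge cause. With no masking described, that judgement may follow exposure: an event at hour 60 is easier to ascribe to octreotide in a patient still on the infusion than in one who stopped at hour 24.

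The missing window matters for a similar reason. Section 15.0 expects that the stay may be shorter with 24 hours. If events are counted for as long as the patient is an inpatient, the 24-hour group could be observed for less time and show fewer events with no true difference. Recall at one month could work the other way and hide a real difference.

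At stake is the between-group safety comparison, which is half of the stated objective. The primary rebleeding analysis is not affected.

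**Working it through.** The plan gives no calculated figure for safety. Its one calculated figure, 69 per group, reproduces at one-sided alpha 0.05: n = (1.645 + 1.282)² × 2 × 0.90 × 0.10 / 0.15² = 68.5, rounded up to 69. This point does not depend on it.

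**Endpoint set against collection**

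| What the endpoint needs | What the plan provides |
|---|---|
| Hyperglycemia (4.0) | No glucose in either laboratory list (10.0) |
| Pneumonia, cardiac, ileus and GI events (4.0) | No complication item in 1 to 11 or 12a to 12e; general adverse event recording (13.0); chart review (10.0) |
| Definitions of events | Section 13.0 refers to definitions without giving them |
| Common counting period | None for this endpoint; rebleeding and survival have 7 and 30 days |
| Judgement of cause | Implied by the endpoint wording; assessor not named, no masking described |

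**Timing of the first scheduled question.** Taking the infusion to start close to the initial visit, 30 − 3 = 27 days after a 72-hour infusion ends and 30 − 1 = 29 days after a 24-hour one. This gap applies to the phone question only, not to chart review or adverse event recording.

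**Effect of unequal attribution (assumed inputs).** Observed rate = any-cause rate × share attributed to octreotide. The any-cause rate is the same in both groups, so the true difference is zero.

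| Any-cause rate | 25% attributed in both groups | 25% attributed (24 h) vs 50% (72 h) |
|---|---|---|
| 10% | 2.5% vs 2.5% | 2.5% vs 5% |
| 20% | 5% vs 5% | 5% vs 10% |
| 30% | 7.5% vs 7.5% | 7.5% vs 15% |

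The apparent difference is 0 to 7.5 percentage points over this range. An any-cause count would show zero in every row.

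**Effect of incomplete capture (assumed rates).** With 80 per group and two-sided 0.05, power = Φ{[|p₁ − p₂| − 1.96√(2p̄(1 − p̄)/80)] / √([p₁(1 − p₁) + p₂(1 − p₂)]/80)}, with both rates multiplied by the share captured.

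| True rates | All captured | Three quarters | Half |
|---|---|---|---|
| 5% vs 10% | 22% | 18% | 13% |
| 10% vs 20% | 42% | 32% | 22% |
| 15% vs 30% | 62% | 48% | 32% |
| 10% vs 30% | 89% | 76% | 56% |

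The documents give no complication rate, attribution share or capture rate, so both tables show the mechanism and do not measure it.

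**The case against.** The strongest reply is that in-hospital harms are already covered. Section 13.0 records all adverse events in both groups and does not limit this to events blamed on octreotide. Charts are reviewed, and every patient is observed in hospital for at least 72 hours after EBL. The data list is introduced as additional, and its admission items also leave out rebleeding, transfusion and TIPS. Read as closed, it would mean that the primary endpoint is not collected in hospital either, so it more plausibly supplements section 4.0. All of this stands. A reader might infer from the list that in-hospital harms are missed or that hyperglycemia cannot be derived; the documents support neither.

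Nor do the documents say who judges cause. That unblinded staff do so is an inference, and the section 4.0 wording could be read simply as the title of a list of events. The absence of described masking and of any rule for attribution is, however, plain in the text.

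A reader might also take section 15.0 to promise fewer octreotide complications with 24 hours. It speaks of avoiding complications of hospitalization and, separately, of less exposure to medication.

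What the reply leaves open is the link. A general rule that sends reports to the IRB sets no items to look for, no glucose collection and no common period, and does not say how reports become the section 4.0 endpoint. Several sites enter data (section 11.0), so unlisted items may be abstracted differently.

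**Conclusion.** The point holds as a worthwhile, inexpensive improvement to a secondary endpoint. The safety endpoint is worded by attribution, no masking is described, no common window is set, and the data list does not name the events or the glucose values that the endpoint needs. Capture and attribution may therefore be incomplete or differ between groups.

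Neither the size nor the direction of any bias can be established from the documents. The 5% versus 10% reading rests wholly on assumed inputs and does not show that the trial will produce a false safety advantage for 24 hours.

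The conclusion assumes that nothing outside the text available here, such as case report forms or the material between sections 6.0 and 8.0, supplies the missing definitions, fields or window. If it does, the point reduces to the attribution wording.

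**What to change.** - **Section 4.0:** define the endpoint as each listed event from any cause, counted from randomization over one fixed window that is the same for both groups regardless of discharge. The first 72 hours is one option, since all patients are then in hospital; day 7, using chart review, is another; both could be reported. The inpatient minimum runs from EBL and randomization follows EBL, so a 72-hour count from randomization may need chart review for its last part. The window should not end at discharge, because a shorter stay in one group would shorten its observation.
- **Attribution:** report relatedness to octreotide descriptively only, and state who judges it.
- **Section 10.0, data list:** add glucose values already in the chart and a dated yes/no field for each listed complication, with short definitions.
- **Phone calls:** use the day-30 and later side-effect questions only as a supplement.

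The cost is protocol wording and a few REDCap fields filled from the chart, with no new tests. The downside is that any-cause counts will be higher and less specific to octreotide, which can dilute a true drug effect; the descriptive attribution column keeps that information visible.

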11.0 Data Management

Statistical Analysis:

The study design is a non-inferiority study. Primary hemostasis of esophageal variceal bleeding is highly successful (90%), despite rebleeding rates of 10-30%. A superiority trial of primary hemostasis would require a very large number of patients, would require significant resources and would take a long time to recruit.

A non-inferiority trial is appropriate to demonstrate that receiving octreotide for 24 hours is not inferior to the standard of care of 72 hours.

Assuming a primary hemostasis rate of 90% and a non-inferiority margin of 15%, 69 patients will be needed in each group to achieve 90% power. This calculation assumes a type I error rate of 0.05 and equal sample sizes. Anticipating patient drop-out of approximately 15%, a sample size of 80 patients will be required.

Qualitative variables in the two groups will be compared using chi-square test with Yates' correction of Fisher's exact test, when applicable, and represented as percentages. The Mann-Whitney test will be used to compare quantitative variables, which will be expressed as means \pm standard deviations (SD).

Factors associated with re-bleeding and complications will be identified. Logistic regression modeling will be used to assess differences in re-bleeding between the two groups adjusting for significant confounding variables.

All data collected from patients at all sites will be entered in a Redcap project that will be created at MUSC. All sites will have access to this project, however each site will only have viewing and editing rights to the subjects that have been entered by that specific site.

Costs and Payments:

All costs associated with the protocol are part of the routine and standard-of-care for patients with variceal hemorrhage. The researchers, the study patients, or the participating sites will not be remunerated for their participation.

13.0 Provisions to Monitor the Data to Ensure the Safety of Subjects (if applicable)

Data Safety Monitoring Board (DSMB):

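### The data list does not name creatinine and leaves INR, ascites grade and encephalopathy grade unspecified, so baseline liver severity is only partly described and the adjusted rebleeding model lacks a standard severity score

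*Combined protocol and SAP*

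**What the plan says.** Section 10.0 (Collected Data) introduces its list with "Additional data collected from medical records during this study will include". The items that bear on liver severity are:

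- laboratory: "complete blood count (CBC), liver function tests, ammonia (if checked per hospital standard of care), hepatitis serologies", with the components of the liver function tests not listed;
- clinical: "Presenting symptoms and physical exam findings";
- imaging: "Imaging findings – liver morphology, patency of portal vein";
- procedures: "Paracentesis".

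The same laboratory line recurs for the follow-up time points. The follow-up calls ask in general terms about "cirrhosis related health complications and possible side effects of octreotide".

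Section 11.0 says that factors associated with rebleeding and complications will be identified. It plans a logistic regression for rebleeding "adjusting for significant confounding variables", without naming the variables. Section 5.0 requires known or suspected cirrhosis and sets no severity class or score limit. Section 10.0 describes blocked randomization after EBL, with no stratification by severity. Section 4.0 makes rebleeding within 72 hours the primary endpoint and survival at 7 and 30 days a secondary one.

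**The concern.** In an all-cirrhosis population, severity of liver disease is the obvious candidate to explain early rebleeding and death. A reader of a non-inferiority result will want to know how sick the patients were and whether the groups were alike in this respect. The plan also promises an adjusted rebleeding model, but its data list does not secure the inputs to a standard severity score. Data are abstracted from charts at several sites, each entering its own patients, so a field that is neither named nor graded is likely to be recorded differently from site to site, or not at all.

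**Working it through.** **Step 1. Compare the list with the scores.** The documents define neither score; the components below are the usual ones.

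| Component | Used in | Position in section 10.0 |
|---|---|---|
| Creatinine | MELD | Under no listed laboratory heading |
| INR | MELD, Child-Pugh | Not named; may or may not be meant by liver function tests |
| Bilirubin | MELD, Child-Pugh | Probably within liver function tests |
| Albumin | Child-Pugh | Probably within liver function tests |
| Ascites grade | Child-Pugh | Not named; exam findings and paracentesis carry part of it, ungraded |
| Encephalopathy grade | Child-Pugh | Not named; exam findings may mention it; ammonia is conditional and is not a grade |

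MELD therefore cannot be formed from the listed items. Child-Pugh could be formed only where a site happened to record INR and enough detail to grade ascites and encephalopathy. The follow-up items do not help, because they postdate randomization and cannot serve as baseline covariates.

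**Step 2. Reproduce the plan's sample size, to fix the scale.** Inputs from section 11.0: 90% in both groups, margin 0.15, power 90%, type I error 0.05 (taken as one-sided).

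n per group = (1.645 + 1.282)² × 2 × 0.90 × 0.10 / 0.15² = 68.5, rounded up to 69, as stated. Then 69 × 1.15 = 79.4, rounded up to 80, which agrees with the total of 160 in section 6.0.

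**Step 3. Chance imbalance in severity (illustration).** Assume 30% of patients are severe; the documents give no figure. Let X and Y be independent binomial counts of severe patients in the two groups, each with n patients and probability 0.30. Summing the exact probabilities:

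- n = 80, more than 10 points apart (|X − Y| ≥ 9): 14.2%
- n = 80, 10 points or more apart (|X − Y| ≥ 8): 19.5%
- n = 69, more than 10 points apart (|X − Y| ≥ 7): 22.7%

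These are two-sided. At n = 80, an imbalance of more than 10 points that favours the 24-hour group occurs in half of 14.2%, about 7%. If 20% to 50% of patients are severe, the same sums for more than 10 points run from 9.2% to 17.9% at n = 80 and from 16.6% to 26.8% at n = 69.

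**Step 4. Effect on the rebleeding difference.** Shift = imbalance × risk gap between severe and other patients (gaps assumed).

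- Gap of 14 points (20% against 6%): 0.10 × 0.14 = 1.4 points, and 1.4 / 15 = 9% of the margin. With 30% severe, these rates average 0.30 × 20% + 0.70 × 6% = 10.2%, in line with the plan's 90% success rate.
- Gap of 25 points: 0.10 × 0.25 = 2.5 points, and 2.5 / 15 = 17% of the margin.

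**The case against.** The strongest reply is that section 10.0 gives a summary under broad headings, not a closed data dictionary, and does not claim to be exhaustive. That stands, and it rules out several stronger readings that a reader might infer.

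- *That severity will be wholly unknown, or that an imbalance could not be seen.* The blood count gives platelets, liver function tests usually give bilirubin and albumin, and exam findings, portal vein patency and paracentesis are recorded. These allow a partial comparison and can enter a model without a composite score. Section 5.0 also bounds the population somewhat: patients must be able to consent, and prior TIPS, a variceal bleed in the last 90 days and recent severe illness are excluded.
- *That the primary comparison is biased.* Randomization protects the unadjusted comparison on average, and chance imbalance is already reflected in its error rate. The shifts above describe what could happen in a single trial; they are not a bias.
- *That the omission is irreparable.* Data come from medical records and remain code-linked to identifiers at the enrolling site (section 5.0), so routine admission values could probably be abstracted again, with extra work at every site.
- *That the plan breaks a promise on survival.* Section 11.0 promises adjusted modelling of rebleeding only.

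What remains is that creatinine lies outside every listed laboratory heading, that three further components are left to each site's reading of general terms, and that no score is named. An open list permits these fields to be collected, but does not ensure that they are collected in the same way everywhere.

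**Conclusion.** The point holds as a gap in specification. With the list as written, MELD cannot be formed and Child-Pugh cannot be formed consistently, so the plan describes baseline severity only in part and its adjusted rebleeding model has no standard severity measure to use. The consequences fall on description, applicability and the adjusted analysis; the validity of the randomized comparison is not in question.

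The size is modest: on the assumed rates, a shift of 9% to 17% of the margin in the minority of trials with an imbalance of about 10 points. The share of severe patients and the risk gaps are assumptions, since the documents give neither. The absence of the four items and of any score is a matter of reading and depends on no assumption beyond the usual definitions of the scores. This is a worthwhile, inexpensive improvement rather than a condition for the trial's validity.

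**What to change.** In section 10.0, add six named baseline fields, using values from before EBL: INR, creatinine, bilirubin, albumin, ascites grade and encephalopathy grade. Name one severity score in advance, derive it for every patient and report it by group.

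In section 11.0, replace the selection of covariates by significance with that single score in the adjusted rebleeding model. Present the result as a supportive standardised risk difference for 72-hour rebleeding, so that it is on the same scale as the 15-point margin. A similar analysis of 30-day survival is an optional addition.

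The cost is a few more chart fields per patient, which an admission work-up would normally supply (an assumption), and one supportive analysis. Some values will be missing, so the handling of a missing component should be stated. The gain in precision for rebleeding will be modest. Treatment, sample size and the unadjusted comparison are unchanged.
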